6.2 Timing of Evaluations

6.2.1 Screening Evaluations

Screening evaluations must occur prior to the participant's starting any study treatment. Screening evaluations to determine eligibility must be completed within 30 days prior to study entry, unless otherwise specified.

The cytology and HPV evaluations cannot be performed while the participant is menstruating. If a participant has visual evidence of bacterial STIs or an examination consistent with pelvic inflammatory disease, then samples for cytology and HPV testing should not be obtained. The participant should be treated according to the local standard of care, in which case screening evaluations can be performed a minimum of 7 days after initiating treatment.

In addition to data being collected on participants who enroll into the study, demographic, clinical, and laboratory data on screening failures will be captured in a Screening Failure Results form and entered into the ACTG database. Cytology, colposcopic visual impression, and HPV testing on screening failures will also be captured on a case report form (CRF) and entered into the ACTG database.

6.2.2 Entry Evaluations

Participants should receive study treatment within 7 days after randomization/registration, unless contraindicated (see Section 6.3.10).

6.2.3 Post Entry Evaluations

Post Entry Evaluations

Study visits will be conducted in the clinic at week 26 +/- 6 weeks for participants in all arms and at weeks 52, 78, and 104 +/- 6 weeks for participants in Arms A and B only. Additional visits will be necessary between these time points to discuss cytology and/or histology test results and subsequent management plans with participants.

Post Cervical Treatment Evaluations

Participants will be seen in the clinic 4 weeks +/- 10 days after cryotherapy or LEEP for assessment of procedure-related AEs.

Study Completion Evaluations

The final study visit will occur at week 26 +/- 6 weeks for participants in Arm C and at week 130 +/- 12 weeks for participants in Arms A and B. The off-study CRF must be completed and keyed into the database for each participant after completing the evaluations required at the final study visit unless CIN2+ is found, in which case the off-study CRF should be completed and keyed into the database after the participant undergoes LEEP and completes the 4-week post treatment assessment of procedure-related AEs.

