Part of this study is being funded by a supplement from the U.S. NIH to conduct implementation science research of interest to the President’s Emergency Plan for AIDS Relief (PEPFAR). The PEPFAR objectives in section 1.3 will use screening and baseline evaluations from all women who give consent for this study. The availability of the **xpert hrHPV** ~~careHPV~~ test should broaden access to cervical cancer screening through the HPV test-and-treat strategy. It will be critical to understand how this test performs in HIV-infected women. ~~Although this assay has been conformité européenne (CE) marked, it will not be widely available until late 2011.~~ This study will compare **xpert hrHPV** ~~careHPV~~ results to two other HPV tests: HPV DNA PCR and aHPV. Cryotherapy is not recommended for women with extensive cervical lesions. Data from our Zambian investigators suggest that 15-20% of HIV-infected women will have such lesions and that half of these women will have CIN2/3 or invasive/microinvasive cancer on histology [40, 41]. Algorithms for cervical cancer screening must address treatment of these women to maximally impact mortality from cervical cancer.

2. Per the March 2015 interim DSMB review, biopsies are being added to study follow-up visits for all participants, regardless of preceding colposcopy results.

- Section 3.0, fourth paragraph, now reads: Participants in Arms A and B will be seen at regular intervals post entry for aHPV, HPV DNA PCR, cervical cytology, and cervical colposcopy and directed biopsies for a total follow-up length of 130 weeks. **At least two cervical biopsies should be performed at the week 78 and week 130 visits. Visible lesions should be biopsied preferentially. If no visible lesions are seen, then two random biopsies should be obtained.**
- Section 6.3.10, subsection on colposcopy and directed biopsies, now reads:

Post entry:

- Participants in Arms A and B will undergo colposcopy and directed biopsies at the weeks 26, 78, and 130 clinic visits. **At least two cervical biopsies should be performed at the week 78 and week 130 visits. Visible lesions should be biopsied preferentially. If no visible lesions are seen, then two random biopsies should be obtained.**
- Participants in Arm C who undergo LEEP post-entry will undergo colposcopy

and directed biopsies at the week 26 clinic visit.

Digital images and colposcopic impression will be submitted for review, along with location of cervical biopsies.

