(The following paragraph supersedes Clarification Memo [CM] #2, dated 01/02/1014.) Directed biopsies will be obtained from areas suspicious for CIN. ~~Biopsies are taken only if lesions are seen upon colposcopy.~~ In the event lesions are not seen upon colposcopy but the cytology specimens show presence of HSIL, then the participant should return to the study clinic for repeat colposcopy and other diagnostics procedures such as endocervical curettage (ECC), random cervical biopsies (**if not already done**), or diagnostic LEEP. Results of these diagnostic tests must be recorded on the appropriate CRF. ~~Slides from biopsies of CIN2+ and biopsies without CIN2+ will be submitted for review.~~ If CIN2+ is detected by biopsy, the participant will undergo LEEP.

- c. Sample Informed Consent, What do I have to do if I am in this Study?, Groups A and B: At the study visit about 6, 18, and 30 months after the entry visit you will also have a colposcopy and biopsies if any abnormal areas are seen. **At months 18 and 30, you will have two biopsies performed whether or not abnormal areas are seen.**

3. Additional clarifications were made to Section 6.3.10.

- a. The subsection, "Diagnoses," now reads:

Diagnoses

(Per CM #1, dated 02/05/1013.) After entry, record any new diagnoses made since the last visit using the ACTG criteria for clinical events and other diseases.

(Per CM #1, dated 02/05/1013.) Except for invasive cancer, cervical cytology and histology results do not need to be recorded as events; these results will be entered on study-specific CRFs only.

(New language) Record all histology results from procedures for the diagnosis or treatment of cervical HSIL (such as cervical conization or hysterectomy) and from biopsies performed related to the presence or absence of squamous intraepithelial lesions on the appropriate CRFs.

- b. The subsection, "LEEP," now reads:

(The following paragraph supersedes item 4b in LoA #2, dated 08/09/1012.)

LEEP

Participants found to have CIN2+ by biopsy at any point during the study will be offered LEEP **or other excisional treatment** (except for participants in Arm A **prior to week 26** who have CIN2+ on pre-cryotherapy biopsy at entry). If the participant had a prior LEEP, treatment of recurrent **or incompletely treated**

CIN2+ is at the discretion of the site investigator. These participants will continue on study.

(No changes to the remainder of this subsection.)

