Participants in Arm A will undergo cervical cryotherapy within 7 days after entry. **Please see the A5282 MOPS for details. All women in Arm A should undergo one or two cervical biopsies immediately prior to cervical cryotherapy. Up to two visible lesions should be biopsied. If no lesions are seen, then one normal-appearing area of the cervix should be biopsied at a location of the investigator's choosing. At least one biopsy is collected.** Digital images obtained immediately prior to and following cryotherapy will be submitted for review.

9. Section 7.3, Other Diseases/Conditions, Invasive Cervical, Vaginal, or Vulvar Cancer, Last Paragraph

Participants who are diagnosed with cervical, vaginal, or vulvar cancer after enrolling into the study will continue to be followed on study. These participants will come into the clinic per the time points in Section 6.1 for study evaluations. These participants will receive additional treatments as indicated in the site-specific clinical management plan. **Any women in Arm A diagnosed with invasive cervical cancer on the biopsies obtained immediately prior to cryotherapy should be seen as soon as possible for evaluation by a local specialist and treated as per standard of care in that country.**

10. Section 9.2.2, Secondary Endpoints

9.2.2.11 Sexual history at baseline (age at first vaginal sex and lifetime number of vaginal sex partners) and recent sexual activity (number of vaginal sex partners and condom use within the previous 6 months).

11. Section 9.6, Analyses

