Haiti (Port-au-Prince)	GHESKIO	470	312	57% by Digene HC2	40%	7%	10%	Unpublished
India (Pune)	NARI	303	343	41% by Digene HC2	34%	6%	16.5%	38
South Africa (Johannesburg)	WITS	1010	231	72% by PCR *	50%	18%	Not assessed	30, 39
Zambia (Lusaka)	University Teaching Hospital	150	165	90% by PCR	76%	52%	Not assessed	36

* PCR performed on a subset of women (n=191) in South Africa.

Potential Risks of Study Treatments

- Cervical biopsies
 - Common, not serious
 - Pain during biopsy
 - Mild bleeding
 - Rare
 - Heavy bleeding requiring treatment to stop the bleeding
 - Infection of the cervix requiring antibiotics
 - Possible increased risk of miscarriage after multiple cervical biopsies
- Cervical cryotherapy
 - Common, not serious
 - Pain and cramping during the procedure (1%)
 - Profuse watery vaginal discharge (>10%)
 - Heavy, odorous discharge (1%)
 - Mild cervical bleeding (2%)
 - Cervical infection (1-2%)
 - Retraction of squamocolumnar junction into cervical canal, which makes subsequent exams more difficult

- Rare
 - Severe cramps and abdominal pain requiring parenteral medications (<1%)
 - Pelvic inflammatory disease (<1%)
 - Heavy cervical bleeding (very rare, potentially serious)
 - Cervical stenosis (very rare, potentially serious)
 - Vaginal injury from unintentional freezing (very rare, not serious)
 - Vasovagal reactions during procedure (<1%)
 - Potential increased risk of transmitting HIV to sexual partners post-procedure
- LEEP
 - Common, not serious
 - Transitory pain from local anesthetic into the cervix
 - Blood tinged, dark brown mucus for 1-2 weeks post LEEP
 - Dull ache/cramping during procedure
 - Postoperative cramping/pain (common, relieved by analgesics)
 - Uncommon, serious:

Intraoperative/perioperative

 - Anesthetic reaction/vasovagal syncope <1%
 - Severe intra/perioperative bleeding <2%
 - Electrical injury of vaginal wall (rare)
 - Perforation of uterus <1%

Postoperative

 - Moderate to severe postoperative bleeding <2%
 - Cervical or endometrial infection/pelvic inflammatory disease (rare, mostly if not treated perioperatively by antibiotics)
 - Cervical stenosis, due to scarring: <1-2%: more in menopausal women
 - Cervical incompetence: resulting in miscarriage or pre-term labor <2%
 - Infertility (rare)
 - Potential increased risk of transmitting HIV to sexual partners post procedure [37]

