Cervical cytology specimens will be obtained and processed locally in real-time (refer to the A5282 MOPS). Pap smears will be interpreted locally. Results should be communicated to the participant's primary care provider, and the site must document this communication in the source documents.

Colposcopy and Directed Biopsies

At entry:

- Participants in Arm A will not have colposcopy and directed biopsies; these women will instead undergo cryotherapy.
- Participants in Arm B will undergo colposcopy with directed biopsies if the screening cytology is abnormal, i.e., the result reveals atypical squamous cells of undetermined significance (ASCUS), atypical glandular cells of undetermined significance (AGUS), low grade squamous intraepithelial lesion (LSIL), or HSIL.
- Participants in Arm C will undergo colposcopy and directed biopsies if the screening cytology shows HSIL or if cervical lesions were seen upon visual inspection.

Post entry:

- Participants in Arms A and B will undergo colposcopy and directed biopsies at the weeks 26, 78, and 130 clinic visits.
- Participants in Arm C who undergo LEEP post-entry will undergo colposcopy and directed biopsies at the week 26 clinic visit.

Digital images and colposcopic impression will be submitted for review, along with location of cervical biopsies.

Directed biopsies will be obtained from areas suspicious for CIN. Biopsies are taken only if lesions are seen upon colposcopy. In the event lesions are not seen upon colposcopy but the cytology specimens show presence of HSIL, then the participant should return to the study clinic for endocervical curettage (ECC). Slides from biopsies of CIN2+ and biopsies without CIN2+ will be submitted for review. If CIN2+ is detected by biopsy, the participant will undergo LEEP.

LEEP

Participants found to have CIN2+ by biopsy at any point during the study will be offered LEEP. If the participant had a prior LEEP, treatment of recurrent CIN2+ is at the discretion of the site investigator. These participants will continue on study. All specimens obtained by LEEP will be fixed in formalin and submitted for review. Digital images obtained immediately prior to and following LEEP will also be submitted for review.

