6.3.11 Questionnaires

Assessment of Targeted AEs

AEs related to cryotherapy or LEEP will be recorded and graded according to the DAIDS "Female Genital Grading Table for Use in Microbicide Studies," which can be found on the DAIDS RSC web site: <http://rsc.tech-res.com/safetyandpharmacovigilance/>.

Sociodemographic and Sexual Behavior Questionnaire

A standardized questionnaire will be used to collect data on sociodemographic indicators as well as sexual behavior indicators (e.g., age at first sexual intercourse, lifetime number of sexual partners, frequency of vaginal intercourse in the preceding 6 months, and number of partners in the preceding 6 months). After entry, only recent sexual activity will be assessed.

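### Targeted AE assessment was not extended to the biopsies added by amendment, so the Arm A cryotherapy AE table may include biopsy harm

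*Protocol*

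**What the plan says.** **Collection of targeted AEs.** Protocol 6.2.3 sets the safety visit: "Participants will be seen in the clinic 4 weeks +/- 10 days after cryotherapy or LEEP for assessment of procedure-related AEs". Section 6.3.11 defines what is recorded: "AEs related to cryotherapy or LEEP will be recorded and graded according to the DAIDS" grading table for female genital events. The Section 6.1 schedule marks targeted AEs only at entry and at the post-treatment visit. Clarification Memo #1 (February 2013) rewrote the signs-and-symptoms text of 6.3.6 after the first added biopsies, and still limits all-grade capture to cryotherapy and LEEP.

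**What the amendments added.**
- Version 1.0 gave Arm A no biopsy at entry. Letter of Amendment #1 (September 2011) changed this: "All women in Arm A should undergo one or two cervical biopsies immediately prior to cervical cryotherapy".
- Version 1.0 already planned later biopsies, "Participants in Arms A and B will undergo colposcopy and directed biopsies at the weeks 26, 78, and 130 clinic visits", but only where a lesion was seen. The letter that followed the March 2015 DSMB review made them mandatory at two visits: "At least two cervical biopsies should be performed at the week 78 and week 130 visits". It adds: "If no visible lesions are seen, then two random biopsies should be obtained".
- The same letter widens treatment of CIN2+ from LEEP to LEEP "or other excisional treatment".

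**Known biopsy risks.** Section 2.1 lists pain and mild bleeding as common. It lists as rare "Heavy bleeding requiring treatment to stop the bleeding" and cervical infection needing antibiotics. It gives no rates for any of these.

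**Reporting.** Objective 1.3.1 is the safety and tolerability of cryotherapy in Arm A, and SAP 2.3 keeps it within the current analysis. SAP 4.2.3 tabulates targeted AEs in Arm A as events after cryotherapy, and SAP 4.2.4 does the same after LEEP. There is no biopsy table and no split by cause. The text of SAP 2.1 describes Arm A as cryotherapy at entry and does not mention the biopsies.

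**The concern.** The amendments changed the procedures but not the safety collection that goes with them. Two consequences follow.

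First, each Arm A woman treated under Letter of Amendment #1 has biopsy and cryotherapy in one session, and the two share pain, bleeding and infection as possible harms. One assessment four weeks later cannot cleanly separate them. The test-and-treat strategy described in Section 2.1 goes from a positive HPV test to ablation, with no biopsy step. A rate that mixes the two procedures but is labelled as following cryotherapy could make cryotherapy look less tolerable than it is, and the SAP gives the reader no sign of this.

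Second, Grade 1-2 harm from a biopsy alone has no route of its own in either arm. After the week 130 biopsies the off-study form follows, unless CIN2+ is found. Some of these women are biopsied with no visible lesion.

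The safety objective is at stake here, not the efficacy result.

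**Working it through.** **No stated figure to reproduce.** The documents give no AE rate for biopsy. Only the denominators can be checked against the plan.

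**Denominators.** Inputs from protocol 9.4: rates 0.20 and 0.06, one-sided 5%, power 90%, continuity-corrected.
- Uncorrected: n' = [1.645·√(2·0.13·0.87) + 1.282·√(0.20·0.80 + 0.06·0.94)]² / 0.14² ≈ 97.
- Corrected: n = (n'/4)·[1 + √(1 + 4/(n'·0.14))]² ≈ 111 per arm, as stated.
- With 20% loss: 111/0.80 = 138.75. The plan enrolls 140 per arm.

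**Possible mixing in Arm A (illustration).** Let c be the cryotherapy rate of an event that both procedures can cause, and b an assumed additional biopsy rate. If the two act independently and every biopsy event is attributed to cryotherapy, the recorded rate is 1 − (1 − c)(1 − b). Section 2.1 gives c = 2% for mild bleeding after cryotherapy. The values of b are assumptions.

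| Assumed b | Recorded rate | Extra women among 140 |
|---|---|---|
| 0.5% | 2.5% | 0.7 |
| 1% | 3.0% | 1.4 |
| 2% | 4.0% | 2.7 |
| 5% | 6.9% | 6.9 |
| 10% | 11.8% | 13.7 |

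If sites attribute every event correctly, the excess is zero for any b.

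**Women with no planned contact after week 130.**
- Retained per arm: 140 × 0.80 = 112, so 224 in total.
- Free of CIN2+ at the planning rates of 6% and 20%: 112 × 0.94 + 112 × 0.80 = 105.3 + 89.6 ≈ 195, or 195/224 = 87%.
- At an assumed rate of non-serious harm of 0.5% to 2%, that is about 1 to 4 events without active follow-up.

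Two cautions apply. The planning rates are cumulative from week 26, so they count CIN2+ found before week 130; on this point alone the count could be somewhat higher, with 224 as its ceiling. In the other direction, the count assumes that every woman reached week 130 after the letter. Working back from March 2015, a woman who entered before about September 2012 had already passed week 130 (30 months), and one who entered before about September 2013 had passed week 78 (18 months). Actual accrual dates are not in the documents.

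**What is still captured, whatever the cause.**
- Grade 3 or higher signs and symptoms, and new diagnoses meeting ACTG criteria, after entry (6.3.6 as revised by Clarification Memo #1), with clinical assessments at weeks 26, 52, 78, 104 and 130 (6.1).
- Serious events by the ICH definition, on the CRF (6.3).
- Expedited reports of Grade 3 and 4 serious events related to study procedures, which include biopsy (11.4.2), for a period set by an external manual (11.4.4).
- DSMB review of overall reported AEs (9.5).

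**The case against.** The case on the other side is substantial, and much of it stands.

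- **A reader might infer that harm from the week 130 biopsies is never collected.** The documents do not support that. Serious events go on the CRF, procedure-related Grade 3 and 4 serious events are reportable, and women treated by LEEP for CIN2+ at week 130 return four weeks later. The length of expedited reporting depends on a manual outside the documents. What remains is non-serious harm that arises after the visit.
- **A reader might infer that biopsy harm does inflate the cryotherapy rate.** That is possible but not shown. Sites are asked for events related to cryotherapy or LEEP, and accurate attribution would remove the excess.
- **A reader might multiply out** 224 women × 2 visits = 448 sessions and × 2 biopsies = 896 biopsies without a four-week assessment. At 20% loss and two biopsies per session, that supposes every retained woman had both visits after the letter. It also counts women with visible lesions, who would have been biopsied under Version 1.0, and women who then had LEEP.
- **The SAP wording can be read as timing rather than cause**, and the safety objective is descriptive. This is fair, but a table that does not mention the biopsy will still be read as the safety of cryotherapy.
- **An Arm B comparator is tempting.** Arm B women biopsied at entry without LEEP were selected by abnormal cytology, are not a randomized contrast and have no four-week assessment. They would not separate the two causes.
- **Other excisional treatment is arguably covered**, because the schedule column and the 6.2.3 subheading speak of cervical treatment in general. The operative sentences still name only cryotherapy and LEEP, so the passages need reconciling.

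**Conclusion.** The concern holds in a limited form. Targeted, all-grade AE assessment was not extended to the biopsies that the letters of amendment added or made mandatory. The Arm A rate in SAP 4.2.3 may therefore include biopsy harm. Its size cannot be stated, since no biopsy AE rate is given, and it is zero under correct attribution.

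Grade 1-2 biopsy harm has no collection route of its own. Non-serious harm arising after the week 130 biopsies has no planned contact unless CIN2+ leads to LEEP. The 195 of 224 rests on the planned size, 20% loss, the 6% and 20% planning rates and all women reaching week 130 after the letter.

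The week 78 and 130 biopsies apply to both arms alike, and the primary CIN2+ comparison is unaffected. This is an inexpensive improvement to data collection and labelling, with no bearing on the trial's main conclusion.

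**What to change.** 1. In protocol 6.3.11 and 6.3.6, define targeted AEs as those related to cervical biopsy, cryotherapy, LEEP or other excisional treatment, and record the procedure to which each AE is attributed.
2. In 6.2.3, ask the existing targeted-AE questions at results visits that already take place. Section 6.2.3 places these between the scheduled visits and promises none after week 130 for women without CIN2+. After week 130, therefore, ask only where a results contact occurs anyway; no new visit is proposed.
3. Reconcile 6.2.3, 6.3.11 and SAP 4.2.4 with the later letter's wording on other excisional treatment.
4. Title the SAP 4.2.3 table as AEs after biopsy plus cryotherapy, show events by attributed procedure where recorded, and state that the two causes cannot be fully separated.

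The cost is amendment and SAP wording, one attribution field, and slightly more minor AEs to record and report. The new title and the statement in item 4 need no new data, so they can be made even if follow-up has ended.

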6.2.4 Discontinuation Evaluations

Evaluations for Randomized/Registered Participants Who Do Not Undergo Study Treatment

Participants who are randomized to Arm A or B or registered to Arm C but do not undergo study treatment will not be discontinued from study. Instead, these participants will be followed on study and should complete the study evaluations as per Section 6.1 up to week 130 (Arms A and B) or week 26 (Arm C).

Premature Study Discontinuation Evaluations

Participants who discontinue study participation prior to the final study visit will be asked to come into the clinic to complete the study evaluations as noted in the "Week 130 (Final Visit) / Disc Evals" column of Section 6.1. The participant will discontinue from the study after completing these evaluations. Refer to Section 8.0 for criteria for discontinuation.

